8.3.2 Change from Baseline to Day 43 (Visit 10) in MG-C score

The complete list of MG-C items and scores are provided in [Table 13–2](#). The total score will be calculated according to the rules set down in [Section 13.2](#). This total score will be used to calculate change from Baseline, in summaries and for efficacy analysis.

The following analyses will be performed:

- Secondary: The same approach as specified in [Section 8.2.2](#) will be implemented.
- Sensitivity: The same approach as [Section 8.2.3.2](#) will be applied.
- Supplemental: The same approach as [Section 8.2.4.1](#) will be applied. The worst MG-C total score is 50.

- Additional: The same approach as [Section 8.2.5](#) will be applied.
- Exploratory: The same approach as [Section 8.2.6](#) will be applied.

8.3.3 Change from Baseline to Day 43 (Visit 10) in QMC score

The complete list of QMG items and scores are provided in [Table 13–1](#). Partially missing total scores will be imputed according to the rules set down in [Section 13.1](#). This total score after single item imputation will be used to calculate change from Baseline, in summaries and for efficacy analysis.

The following analyses will be performed:

- Secondary: The same approach as specified in [Section 8.2.2](#) will be implemented.
- Sensitivity: The same approach as [Section 8.2.3.2](#) will be applied.
- Supplemental: The same approach as [Section 8.2.4.1](#) will be applied. The worst QMG total score is 39.
- Additional: The same approach as [Section 8.2.5](#) will be applied.
- Exploratory: The same approach as [Section 8.2.6](#) will be applied.

8.3.4 Change from Baseline in PRO Muscle Weakness Fatigability score

The PRO Muscle Weakness Fatigability score is based on the MG symptoms PRO instrument items 34-42. See [Section 13.4](#) for the complete list of MG symptoms PRO items and scoring details.

The following analyses will be performed:

- Secondary: The same approach as specified in [Section 8.2.2](#) will be implemented.
- Sensitivity: The same approach as [Section 8.2.3.2](#) will be applied.
- Supplemental: The same approach as [Section 8.2.4.1](#) will be applied. The worst PRO Muscle Weakness Fatigability score is 100.
- Additional: The same approach as [Section 8.2.5](#) will be applied.
- Exploratory: The same approach as [Section 8.2.6](#) will be applied.

8.3.5 Change from Baseline in PRO Physical Fatigue score

The PRO Physical Fatigue score is based on the MG symptoms PRO instrument items 19-33.

The same stage-wise MMRM model and analysis approach as specified in [Section 8.2.2](#) will be implemented to test for superiority.

The following analyses will be performed:

- Secondary: The same approach as specified in [Section 8.2.2](#) will be implemented.
- Sensitivity: The same approach as [Section 8.2.3.2](#) will be applied.
- Supplemental: The same approach as [Section 8.2.4.1](#) will be applied. The worst PRO Physical Fatigue score is 100.

- Additional: The same approach as [Section 8.2.5](#) will be applied.
- Exploratory: The same approach as [Section 8.2.6](#) will be applied.

8.3.6 Change from Baseline in PRO Bulbar Symptoms score

The PRO Bulbar Symptoms score is based on the MG symptoms PRO instrument items 6-15.

The following analyses will be performed:

- Secondary: The same approach as specified in [Section 8.2.2](#) will be implemented.
- Sensitivity: The same approach as [Section 8.2.3.2](#) will be applied.
- Supplemental: The same approach as [Section 8.2.4.1](#) will be applied. The worst PRO Bulbar Symptoms score is 100.
- Additional: The same approach as [Section 8.2.5](#) will be applied.
- Exploratory: The same approach as [Section 8.2.6](#) will be applied.

8.4 Analysis of other efficacy endpoints

All other efficacy variables will be summarized overall using descriptive statistics, unless specified otherwise. No stage-wise summary will be performed, except for time to MG-ADL response. Missing data will be handled as described in [Section 4.2.1](#).

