2.4 Determination of sample size

As detailed in [Section 4.4](#), this study will consist of 2 stages, with a formal interim analysis at the end of Stage 1.

Based on historical data, the mean difference in adjusted changes from Baseline of MG-ADL at Day 43, between rozanolixizumab and placebo, is assumed to be 1.5 to 2.0 and the standard deviation is assumed to be 3.5 to 4. A difference of >1.5 could be judged to be clinically meaningful.

It is proposed that the interim analysis will be conducted when approximately 90 eligible study participants have been treated and are evaluable for the primary endpoint, i.e., approximately 30 study participants per dose group in Stage 1. If the study is not stopped for futility after Stage 1, the sample size will be increased, subject to a maximum cap, to provide an overall conditional power target of 90% based on the observed effect size in Stage 1. For each dose that is not futile, the comparison-wise conditional power will be calculated which is the probability of, given the observed data, to achieve a significant result for the completed trial if only the considered treatment is selected. If two doses are selected, then the conditional power associated with the higher treatment effect will be used to determine the stage 2 sample size. Conditional power will be calculated as described in formula 7.2 of Wassmer and Brannath (2016). Similarly, the stage 2 sample size required to achieve a target conditional power of 90% will be calculated using a formula derived from formula 7.4 of Wassmer and Brannath (2016) as follows:

$$\text{Second stage sample size per arm} = 2 * SD^2 * [\phi^{-1}(TP) + \phi^{-1}(1-CRP)]^2 / \Delta^2$$

Where,

SD = pooled standard deviation from the stage 1 statistical model using all dose groups

TP = target conditional power = 0.9

CRP = Conditional rejection probability at stage 1 for the dose group being considered

Delta = assumed true treatment effect for second stage data

If two doses are considered for stage 2 then the above formula will be applied with the conditional error divided by two, to account for multiplicity. Depending upon the selection of one, or two, of the doses after Stage 1, a further 60 to up to a maximum of 150 eligible study participants will be randomized in Stage 2 of the study. Thus, the total sample size of the study could range between 150 and 240 study participants if the study is not futile at Stage 1.

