The power of the study using the above adaptive design and expected sample sizes with a sample size cap of 80 per arm and various scenarios of true treatment effect and standard deviation were determined from a stimulation study using the statistical software ADDPLAN MC, the results of which are summarized in [Table 2-1](#).

The simulation results also indicate that across the various scenarios the average sample size for the study ranges between 169 and 203 study participants. The power for scenarios 5 to 7 and 12 to 14, that is, when the high dose has an effect compared to placebo of 2 points, are at least 80%, indicating that the sample size re-assessment process helps maintain reasonable power when only one dose has a clinically meaningful effect of 2 and the data variability is greater than anticipated (standard deviation[SD]=4).

The chances of stopping the study for futility i.e. both doses individually futile, when at least one dose has a clinically meaningful true effect of 2 or more versus placebo, is less than 3%.

These results support the strategy of entering 30 eligible study participants per dose group in Stage 1 and between 30 to 50 study participants per dose group in Stage 2. Note that ADDPLAN MC implements the sample size increase rule 'per arm' rather than 'per stage', so that if only one dose is selected for Stage 2, then the maximum sample size for this stage is 100, whereas if two

doses are selected than the maximum Stage 2 sample size is 150. Therefore, if an overall study sample size cap of 240 (i.e., 150 in Stage 2) were implemented, irrespective of whether one or two doses are selected, then we would expect power for each scenario to be slightly increased compared to those contained in [Table 2-1](#).

Table 2-1: Simulation results from ADDPLAN MC (x100,000 simulations per scenario) with a capped maximum sample size of 80 per arm using a Bonferroni intersection test

Scenario	Treatment Effect		Standard Deviation	Power	Interim			Average Sample Size
	Dose 1	Dose 2			Proportion Futility	Proportion Selecting Low Dose	Proportion Selecting High Dose	
1	0.0	0.0	3.5	0.020	0.335	0.474	0.474	169.0
2	1.0	1.0		0.400	0.049	0.781	0.782	203.3
3	1.0	1.5		0.632	0.023	0.657	0.914	199.1
4	1.5	1.5		0.750	0.011	0.838	0.841	199.8
5	1.0	2.0		0.864	0.008	0.474	0.975	186.4
6	1.5	2.0		0.892	0.004	0.697	0.942	191.7
7	2.0	2.0		0.943	0.002	0.859	0.860	189.9
8	0.0	0.0	4.0	0.020	0.335	0.467	0.463	168.1
9	1.0	1.0		0.315	0.066	0.734	0.733	199.9

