Protocol deviations will be considered for the interim analysis; thus, it will be required to schedule a data evaluation meeting (DEM) prior to the interim analysis. Protocol deviations will not be considered for the periodic data reviews.

At IA, stage 1 data will be presented to and reviewed by the IDMC and the following decisions will be made:

1. Early stopping for futility: if there is no evidence of either dose of rozanolixizumab being effective compared to placebo.

Notes: the non-binding futility stopping rule will require that the nominal Stage 1 p-value of each dose to be greater than 0.5 (1-sided). This corresponds to both estimated treatment effects being in the wrong direction, i.e., inferiority.

2. Move to the next stage:

Before moving to the next stage, the following will be considered:

- 2.1 Dose Selection: If the study is not stopped for futility (not established), then the “best dose” of rozanolixizumab (and the other active dose if the mean response is not worse than 1 point than the selected “best dose”) will be selected for Stage 2 of the study.

This approach allows selection of the dose with the largest effect defined in terms of the observed mean responses and any doses with a mean response no worse than the best dose by 1 point providing that they are not dropped due to futility, i.e., to be retained nominal 1-sided p-value must be less than 0.5. However, this may not be the sole criterion for selecting the dose, since, additionally, the IDMC will take account other factors, including safety, for the assessment of overall benefit-risk, which will be detailed in the IDMC charter.

- 2.2 Sample size re-estimation: it will be conducted during the IA, as mentioned in [Section 2.4](#).

Note: Early Stopping for Efficacy will not be considered during the IA hence no alpha spending function will be implemented.

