6 DEMOGRAPHICS AND OTHER BASELINE CHARACTERISTICS

6.1 Demographics

Demographic variables will be summarized on the RS, by categories mentioned below using descriptive statistics by treatment group, RLZ total and overall. The same summary will also be presented by stages.

Categories for continuous variables (including n, mean, SD, Median, Min and Max):

- Age at the time of study entry (years) as captured on Demographics CRF

Notes: Missing age will be calculated as year of informed consent signed – year of birth

- Height (cm)
- Weight (kg)

- Body Mass Index (BMI) (kg/m^2) calculated as: $BMI = \frac{\text{Weight (kg)}}{(\text{Height (m)})^2}$

Categorical variables (using frequency counts and percentages):

- Age (18 to <65, 65 to <85, ≥ 85 years)
- Age (≤ 18 , 19 to <65, ≥ 65 years)
- BMI ($<30 \text{ kg}/\text{m}^2$, $\geq 30 \text{ kg}/\text{m}^2$)
- Bodyweight (<50kg, 50kg to <70 kg, 70kg to <100kg, $\geq 100\text{kg}$)
- Bodyweight (<50kg, $\geq 50\text{kg}$)
- Bodyweight (<70kg, $\geq 70\text{kg}$)
- Sex (Male, Female)
- Race (American Indian or Alaska native, Asian, Black, Native Hawaiian or Other Pacific Islander, White, Other/Mixed)
- Ethnicity (Hispanic or Latino, Not Hispanic or Latino)
- Region (North America, Europe, Asia [excluding Japan], Japan)
- Country

Additional subgroup summary of above variables will be presented by pre-, during and post- the COVID-19 pandemic based on the enrolled date relative to the pandemic cut-off date.

For subgroup summary by weight subgroups and total for the administered dose and RLZ total, following variables will be analyzed:

- Age at the time of study entry (years) as captured on Demographics CRF
- Sex (Male, Female)
- Weight (kg)
- Region (North America, Europe, Asia [excluding Japan], Japan)

A by-participant listing of demographics will be provided using the RS. Childbearing potential and lifestyle will be listed using the ES separately.

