10 SAFETY ANALYSES

All safety analyses will be presented using the SS. Listings will be presented by treatment group and study participant; tabulations will be presented by treatment group and RLZ total.

Unless otherwise specified, safety analyses will be presented by treatment group as defined in [Section 3.6](#).

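### If one dose is dropped at the interim, the SAP still pools both stages for most other efficacy summaries and, by silence, for safety, so that dose is set against partly non-concurrent placebo

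*SAP*

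**What the plan says.** SAP 4.4.1 carries the better dose into Stage 2, with "the other active dose if the mean response is not worse than 1 point" behind it and provided it is not futile. One dose may therefore stop. SAP 2.4 plans "approximately 30 study participants per dose group in Stage 1" and "between 30 to 50 study participants per dose group in Stage 2", and adds that "if only one dose is selected for Stage 2, then the maximum sample size for this stage is 100".

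Stage is respected in many places. The primary and continuous secondary endpoints use stage-wise models (SAP 8.2.2, 8.3.2 to 8.3.6). The Day 43 MG-ADL responder analysis is done for each stage (8.3.1). For demographics, SAP 6.1 states "The same summary will also be presented by stages", and 6.2 does the same for baseline characteristics.

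For the other efficacy endpoints the rule is different: "No stage-wise summary will be performed, except for time to MG-ADL response". For safety, SAP Section 10 says only that "tabulations will be presented by treatment group and RLZ total". SAP 4.9.1 plans no subgroup analysis of safety variables, and 4.9.2 limits its pandemic-period summaries to disposition, demographics and baseline characteristics. Neither document says how a dropped dose is to be shown against placebo or counted in RLZ total.

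**The concern.** Most of the pooled tables are descriptive, but three contain between-arm contrasts: TEAEs by risk difference with a 5% threshold (SAP 10.2.2), AEs of focus by risk difference (10.2.3), and the nominal chi-square p-value for rescue use, each dose against placebo (8.4.1). The SAP does not name the comparator for the risk differences; I read it as placebo.

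After a drop, the stopped dose contributes essentially Stage 1 participants, while placebo contributes both stages. The active to placebo ratio also moves from 2:1 in Stage 1 to 1:1 in Stage 2, so RLZ total and placebo have different stage mixes. If event rates differ between stages for reasons unrelated to treatment, part of that difference appears as a drug effect or hides one. A reader could see a stage imbalance at baseline but would have no table showing its effect on adverse events or rescue use.

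**Working it through.** **Inputs.** Stage 1 has 30 per arm in three arms. Stage 2 has n2 = 30 to 50 per arm, so a one-dose Stage 2 has 60 to 100 participants, split equally (SAP 2.4). Evaluable numbers are used throughout.

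**1. The plan's own figures.** The sample-size range reproduces: 3×30 + 2×30 = 150 and 3×30 + 3×50 = 240. An independent simulation of the design, 100,000 runs per scenario, reproduces all 14 rows of Table 2-1. Power agrees within 0.017, average sample size within 1.2 participants, and futility and selection proportions within 0.005.

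**2. How often one dose continues alone.** Write F for futility, L and H for the proportions selecting the low and high dose. Since L + H = P(one) + 2·P(two) and P(one) + P(two) = 1 − F:

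P(exactly one) = 2(1 − F) − L − H

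- Scenario 7: 2(0.998) − 0.859 − 0.860 = 0.277 (the lowest of the 14)
- Scenario 5: 2(0.992) − 0.474 − 0.975 = 0.535
- Scenario 12: 2(0.984) − 0.468 − 0.953 = 0.547 (the highest)

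**3. Stage mix after a drop.**

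| | n2 = 30 | n2 = 50 |
|---|---|---|
| Dropped dose | 30 | 30 |
| Placebo, pooled | 60 | 80 |
| Placebo from Stage 2 | 30/60 = 50% | 50/80 = 62.5% |
| RLZ total, pooled | 90 | 110 |
| Stage 1 share, RLZ total | 60/90 = 66.7% | 60/110 = 54.5% |
| Stage 1 share, placebo | 30/60 = 50.0% | 30/80 = 37.5% |
| Gap in Stage 1 share | 16.7 points | 17.0 points |

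The continuing dose has 30 + n2 participants, as placebo does, with the same Stage 1 share, so the gap is zero. If both doses continue, RLZ total and placebo also match: 60/120 and 30/60, or 60/160 and 30/80.

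SAP 2.4 also considers what would follow "if an overall study sample size cap of 240 (i.e., 150 in Stage 2) were implemented". With 75 per arm (equal split assumed), the Stage 2 share of placebo would be 75/105 = 71%.

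**4. What a stage shift does, with no drug effect.** The spurious difference is the shift multiplied by the Stage 2 placebo share (dropped dose) or by the gap in Stage 1 share (RLZ total). With an assumed fall from 50% to 40% between stages:

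- Dropped dose: 10 × 0.50 = 5.0 points, up to 10 × 0.625 = 6.25 points
- RLZ total: 10 × 0.167 to 10 × 0.170 = 1.7 points

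To reach the 5% display threshold from drift alone, the dropped dose needs a shift of 5/0.625 = 8 to 5/0.50 = 10 points. RLZ total needs 5/0.170 = 29 to 5/0.167 = 30 points.

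**5. Rescue chi-square, dropped dose against pooled placebo, no drug effect (simulated, assumed rescue rates).** The false-positive rate at nominal two-sided 0.05 is 4.4% to 4.7% with 10% rescue in both stages. It is 8% to 10% if rescue rises from 10% to 20%, and 10% to 16% if it falls from 20% to 10%.

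**The case against.** Several stronger readings are tempting, and the documents do not support them.

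- A reader might infer that the sentence in SAP 8.4 governs safety. It covers efficacy only, and it exempts time to MG-ADL response, which 8.4.3 reports for Stage 1, Stage 2 and overall. Pooling of safety follows from the silence of Section 10.
- A reader might infer that randomised comparability is lost across the safety tables. It is not: the continuing dose and placebo share the same stage mix, and the RLZ total distortion is about one sixth of any shift.
- A reader might infer that dose choice is compromised. Selection is made at the interim on Stage 1 data with concurrent placebo, and the interim package includes adverse events (SAP 4.4.2.2).
- A reader might treat the dropped dose as confined to Stage 1. Enrolment is not halted during the interim review (SAP 4.4.1, Protocol 9.8.1), and the randomisation lists change only after the dose decision (Protocol 9.8.3). If m participants per arm are randomised in that interval, the non-concurrent placebo share falls to (n2 − m)/(30 + n2). The documents do not give m, so 50% to 62.5% is an upper bound for n2 of 30 to 50.

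It is also fair to say that no stage shift is documented, that the 5% figure is a display filter and not a decision rule, and that sampling error is larger than the illustrated bias. At 50% incidence the standard error for 30 versus 60 is √(0.25/30 + 0.25/60) = 11.2 points, and for 30 versus 80 it is 10.7. The repeated efficacy summaries for COVID-19-free participants address one possible source of drift, for efficacy only.

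What remains is the dropped-dose contrast, a smaller effect on RLZ total, and no rule for either.

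**Conclusion.** The concern holds in limited form. If exactly one dose continues, which Table 2-1 puts at 27.7% to 54.7% depending on scenario, the planned pooling passes 50% to 62.5% of any stage shift into the dropped-dose contrasts, and about 17% into RLZ total versus placebo. These figures assume 30 per arm in Stage 1, 30 to 50 per arm in Stage 2, and no randomisation to the dropped dose after the Stage 1 cohort. With no shift between stages there is no bias; the 10-point illustration is mine. The SAP expects enough change over time to plan summaries before, during and after the pandemic, so a shift is plausible, but it is not shown. The continuing dose, the primary and secondary inference, and a trial in which both doses continue are unaffected.

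**What to change.** Add one conditional paragraph to SAP 8.4 and Section 10, applying only if a dose is dropped:

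- Present the dropped dose against concurrently randomised placebo, meaning everyone randomised while that dose was still open, including those randomised during the interim review. Do this for the key TEAE and AEOF risk-difference tables and for rescue use. Stage 1 placebo alone would be the wrong comparator for participants added during the review.
- Give the RLZ total versus placebo risk difference stratified by stage, or by whether the dropped dose was open, with Mantel-Haenszel weights. The second is cleaner if there is any overrun. Without overrun the two coincide, and a common stage shift then contributes nothing to the estimate.

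Continuing doses need no change, and nothing changes if both doses go forward. The cost is a few extra tables and some precision: at 50% incidence the dropped-dose standard error rises from about 11 points to √(0.25/30 + 0.25/30) = 12.9 points. Fixing the rule in advance also avoids choosing the placebo comparator after the safety data have been seen.

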8.4.1 Use of rescue therapy due to worsening (IVIg, PEX)

The use of rescue therapy will be identified by a 'yes' response to the "Rescue Medication?" question on the concomitant medication CRF, or plasma exchange as collected on concomitant medical procedure CRF".

The number of study participants in each treatment group that use rescue therapy due to worsening (IVIg, PEX) will be summarized by treatment group and RLZ total.

The nominal p-value (calculated using a Pearson's Chi-Squared test for independence) will be presented for the difference between each rozanolixizumab dose and placebo in the percent of study participants using rescue therapy at a 2-sided 0.05 alpha level.

8.4.2 Time to first rescue therapy

Time to first rescue therapy (in days) is defined as: Date of first rescue therapy use-- Date of first IMP + 1.

Time to first rescue therapy will be estimated and presented using the Kaplan-Meier product-limit method for each treatment. Study participants who do not take rescue therapy will be censored at the date of withdrawal/study completion. Where there are several AEs which led to drop out, consider the earliest starting AE.

The number of study participants with first rescue therapy and number of censored study participants up to 8, 12, 24, 32, 43, 57, 71, 85, 99 days will be summarized using descriptive statistics.

The median time to first rescue therapy, including the two-sided 95% CI, will be calculated for each treatment.

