The maximum duration of MG0003 study per study participants will be up to 18 weeks, consisting of a Screening Period (1 to 28 days to account for central laboratory turn-around time), a Treatment Period (6 weeks), and a blinded Observation Period (8 weeks).

[figure not shown]
1. All study participants who complete the 6-week Treatment Period may roll over into an 8-week Observation Period.
2. All eligible study participants who complete the Observation Period will be invited to be re-randomized into an OLE study to either active dose arm 1 or 2.
3. Study participants who experience disease worsening during the 6-week Treatment Period (e.g., an increase of 2 points on the MG-ADL or 3 points on the QMG scale between two consecutive visits) may be considered for rescue therapy (IVIg or PEX) at the discretion of the Investigator.
4. Study participants who need rescue therapy during the 6-week Treatment Period will receive IVIg or PEX and complete any subsequent visit(s). No further infusions of rozanolixizumab will be administered after initiation of rescue therapy. Once the participant completes Visit 10, he or she will move into the 8-week Observation Period.
5. Study participants who complete the Treatment Period and require initiation of rescue therapy after they start the 8-week Observation Period, may either opt to receive IVIg or PEX or complete the EOS visit and immediately roll over into an OLE study where the participant

will receive rozanolixizumab. Participants who opt to receive IVIg or PEX will complete any remaining visits in the Observation Period and will not be invited to join an OLE study.

6. Study participants who did not complete the 6-week Treatment Period because they needed rescue therapy and require initiation of a second course of rescue therapy while in the 8-week Observation Period can roll over to an OLE study if a minimum of 2 weeks have lapsed since completion of the last IVIg or PEX session. The EOS visit must be completed before enrolling into an OLE study. Alternatively, they can be treated with IVIg or PEX. Study participants who opt to receive IVIg or PEX will complete any remaining visits in the Observation Period and will not be invited to join an OLE study.
7. Study participants who discontinue study medication for any reason other than requiring rescue therapy will not be eligible for enrollment into an OLE study.

A schematic diagram of the study is provided in [Figure 2-1](#).

FIGURE 2-1: STUDY SCHEMATIC

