5 STUDY POPULATION CHARACTERISTICS

5.1 Participant disposition

The following outputs will be created.

Summaries:

- **Reasons for screen failures** (as collected on the Study Termination Screen Failure Case Report Form [CRF] page) will be summarized using the ES for overall. Additionally, the reasons for screen failures will be summarized by pre-, during and post- the COVID-19 pandemic based on the screen failure date relative to the pandemic cut-off date.
- **Disposition of study participants screened** will be summarized using the ES for overall, by region and by site. In this summary, the site number, principal investigator name, first

participant in date, last participant out date, will be captured by randomized treatment and by each analysis set (RS, SS, FAS and PK-PPS).

- **Disposition of analysis sets** will be summarized by treatment groups, RLZ total and by analysis sets (RS, SS, FAS and PK-PPS) using the RS.
- **Disposition and discontinuation reasons** using the RS will contain the number and percentage of study participants who started, completed and permanently discontinued Treatment Period / Observation Period overall and by pre-, during and post- the COVID-19 pandemic based on the start, completed and discontinuation date relative to the pandemic cut-off date. The discontinuation reason in each period will also be summarized. Discontinuation due to COVID-19 pandemic and mandatory withdrawal due to need for rescue therapy and roll over to extension study will be listed as sub-category under “Other” reason.
- **Discontinuation due to AEs** using the RS will summarize the total number of study participants who discontinued the study due to AEs by treatment group, RLZ total and the categories: AE serious fatal, AE non-fatal and other AE non-serious fatal.
- **Count of participants by visit** using RS will summarize the number of participants at each visit by treatment group.
- **Impact of COVID-19 for any reason** using the RS will summarize number and percentage of study participants in each impact category by visit.

Listings of study participant disposition, study discontinuation and study participants who did not meet study eligibility criteria will be provided.

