
3.9 Changes to protocol-defined analysis
	
Add “estimand and ICE strategies to be based on regulatory feedback”.
 
Update Potential Hy’s Law to Alanine Aminotransferase (ALT) or Aspartate Aminotransferase (AST) >3x Upper Limit of Normal (ULN) and total Bilirubin (TBL) >2xULN, and Alkaline Phosphatase (ALP) <2 x ULN.
 
The Full Analysis Set (FAS) will consist of all study participants in the RS.
 
Update MG specific autoantibodies stratification factor from a single two category factor to two binary factors, MuSK (+/-) and aChR (+/-).
 
Minimal Symptom Expression (MG-ADL score of 0 or 1) at any time up to and include both treatment and observation phase, where the protocol only states to include up to Day43 (Visit10).
	
Update as PD to PA4

4.1 Adjustment for covariates
	
Change MG-specific autoantibody stratification factor in statical modeling to be based on values evaluated at Baseline instead of IWRS at randomization.
 
Add explanation on handling of missing MG-specific autoantibody stratification factors.
	
Updated to provide further clarification on source of the baseline MG-specific autoantibody values as stratification factor.

4.4.2.2 Data required for interim analysis
	
Remove MG Symptoms PRO tables from IA list
	
Updated to meet IA meeting decision, not necessary for IA and for DMC.

4.9 Examination of subgroups
	
Change MG-specific autoantibody stratification factor in the subgroup analysis to be based on values evaluated at Baseline instead of IWRS at randomization.
	
Updated to provide further clarification. On source of the baseline MG-specific autoantibody values as stratification factor.

	For Baseline Characteristics table, MG-ADL cut off value was set to be <5, >=5	Updated to set cutoff value for clarification.
5.1 Participant Disposition	Add primary reason for participants roll over from MG3 to MG4/7. “Mandatory withdrawal due to need for rescue therapy and roll over to extension study” to be under “Other”.	Add explanation for participants that has completed the treatment in MG0003 and then needs rescue treatment and instead roll over to the MG0004/7 extension studies.
5.1, 6.1, 6.2, 6.3 8.1, 8.3.1, 8.4.1, 8.4.3-8.4.20 9.1, 9.2, 9.2.1, 9.2.2, 9.3.2, 9.4.1-9.4.4 10.1	Add “RLZ total” as a group for all summaries and plots	General update.

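### SAP 8.4.2 censors exits to the open-label study made because rescue is needed, so after about Day 43 the rescue curve measures neither need for rescue nor actual IVIg/PEX use (minor, descriptive)

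*SAP*

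**What the plan says.** SAP 8.4.2 gives the method: "Time to first rescue therapy will be estimated and presented using the Kaplan-Meier product-limit method for each treatment". The censoring rule is "Study participants who do not take rescue therapy will be censored at the date of withdrawal/study completion". There is also a median: "The median time to first rescue therapy, including the two-sided 95% CI, will be calculated for each treatment". Events are tabulated together with the "number of censored study participants up to 8, 12, 24, 32, 43, 57, 71, 85, 99 days", so the analysis runs through the whole Observation Period. No competing event is named.

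Rescue means IVIg or PEX only (Protocol 6.5.4). SAP 8.4.1 identifies it from the rescue-medication item on the concomitant medication form or from plasma exchange on the procedure form. Open-label rozanolixizumab is neither.

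The route differs by period (SAP 2.3). In the Treatment Period, "Study participants who need rescue therapy during the 6-week Treatment Period will receive IVIg or PEX". In the Observation Period, those who completed treatment and need rescue "may either opt to receive IVIg or PEX or complete the EOS visit and immediately roll over into an OLE study". Those who choose IVIg or PEX lose the invitation to the extension.

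SAP 5.1 already separates this exit in the disposition table, as "mandatory withdrawal due to need for rescue therapy and roll over to extension study". The rationale in SAP 14.2 describes "participants that has completed the treatment in MG0003 and then needs rescue treatment and instead roll over to the MG0004/7 extension studies". SAP 8.4.2 does not use this category.

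**The concern.** Kaplan-Meier treats a censored participant as having the same future risk of the event as those still followed. A participant who leaves because rescue is needed now is plainly at higher risk than those who stay, and after leaving cannot have an in-study IVIg/PEX event. The exit is therefore a competing event for use, and a failure if the quantity of interest is need. Censoring it makes the curve wrong in opposite directions for the two readings: too low for need and, in general, too high for use. The reader is not told which reading is meant. At stake is one descriptive curve after about Day 43, and its median if it is reached there.

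**Working it through.** The plan states no rescue rate for this endpoint, so there is no figure to reproduce. The direction can be derived without rates. The size needs assumptions.

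**Direction.** Let KM be the Kaplan-Meier survivor estimate for IVIg/PEX with rollover censored, S the survivor estimate for IVIg/PEX or rollover for need, and dL the estimated hazard of IVIg/PEX use. Then:

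- 1 − KM = sum of KM(u−)·dL(u)
- cumulative incidence of use = sum of S(u−)·dL(u)
- proportion needing rescue = 1 − S

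S cannot exceed KM. So cumulative incidence of use ≤ 1 − KM ≤ proportion needing rescue. The second inequality is strict once any rollover for need has occurred. The first is strict once a rollover precedes a later IVIg/PEX event. In 16,000 simulated arms (four settings of 4,000, with 30 or 60 participants and 5% other dropout), 1 − KM was never below cumulative incidence. It was strictly above it in 80% to 99.95% of arms, depending on the setting.

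**Size, on assumed rates for one arm.** Hazards are constant from Day 43 to Day 99. Let a = 5% be rescued by Day 43, b the share of the rest who later need rescue, and s the share of those who roll over. At Day 99:

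- curve as planned = 1 − (1 − a)(1 − b)^(1 − s)
- actual use = a + (1 − a)(1 − s)b
- need = a + (1 − a)b

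Example with b = 60%, s = 50%: the curve is 1 − 0.95 × 0.40^0.5 = 39.92%; use is 0.05 + 0.95 × 0.5 × 0.6 = 33.50%; need is 0.05 + 0.95 × 0.6 = 62.0%.

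| b | s | Curve % | Use % | Need % | Use overstated (points) | Need understated (points) |
|---|---|---|---|---|---|---|
| 30% | 50% | 20.52 | 19.25 | 33.5 | 1.27 | 13.0 |
| 30% | 80% | 11.54 | 10.70 | 33.5 | 0.84 | 22.0 |
| 60% | 50% | 39.92 | 33.50 | 62.0 | 6.42 | 22.1 |
| 60% | 80% | 20.91 | 16.40 | 62.0 | 4.51 | 41.1 |

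With b = 10% the overstatement of use is only 0.13 points (s = 50%) or 0.08 (s = 80%). With s = 95% it is 0.25 points (b = 30%) or 1.4 (b = 60%).

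**Build-up over time.** For b = 60%, s = 50%, the curve against actual use is 15.3% v 14.7% at Day 57, 24.4% v 22.5% at Day 71, 32.6% v 28.6% at Day 85 and 39.9% v 33.5% at Day 99.

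**Median.** It is not reached in any of the four cases. Setting the curve to 0.5 at Day 99 gives b = 72% for s = 50% (actual use then 39.3%) and b = 96% for s = 80% (actual use 23.2%).

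**Scale.** The 95% half-width 1.96·√(p(1 − p)/80), for use between 10.7% and 33.5% at the cap of 80 per arm (SAP 2.4), is 6.8 to 10.3 points. In each of the four cases the overstatement of use is below the half-width for that arm; the understatement of need is not below 10.3 points in any of them.

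**The case against.** The strongest reply is that actual use is already reported without bias. SAP 8.4.1 gives the number using rescue by arm, SAP 8.4.2 tabulates first-rescue counts by day, and nothing says that the curve is to be read as a proportion of users. SAP 5.1 also shows the number of rollovers for need by period. All of this stands: the counts of recorded use are right, and only a split of the censored counts by day is missing. It does not rescue the curve or the median, which carry no label saying what they estimate.

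A second reply is that Kaplan-Meier could target a hypothetical setting without rollover. That would need exits unrelated to the risk of rescue. Here the need for rescue is the reason for the exit.

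A third is that replacing the curve by cumulative incidence of use alone would make matters worse for anyone reading it as need. This is correct: in the four cases that estimate falls short of need by 14.3, 22.8, 28.5 and 45.6 points, more than the planned curve does. The remedy therefore has to be paired.

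A reader might infer that the plan certainly overstates IVIg/PEX use, or that it distorts the comparison between arms. The documents do not support either. The overstatement is zero if no rollover precedes a later IVIg/PEX event, and with no rescue or rollover rates by arm neither the direction nor the size of any between-arm effect can be stated.

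**Conclusion.** The point holds as a minor correction to one descriptive analysis. Conditional on at least one rollover for need of rescue, the curve understates need from about Day 43. Conditional on a rollover preceding a later IVIg/PEX event, it overstates use. Those directions follow from the documents. The sizes, about 13 to 41 points for need and 0.8 to 6.4 for use at Day 99, rest on the assumed rates and constant hazards; at 10% later need the overstatement of use is about 0.1 point.

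Results before about Day 43 are essentially unaffected, because need in the Treatment Period leads to IVIg or PEX. The boundary is approximate because Visit 10 has a window of two days either side. It would be wrong to read this as a flaw in SAP 8.4.1, in the tabulated counts of use, or in any tested result: time to first rescue is an *other* endpoint, summarised descriptively under SAP 8.4, with no between-arm test of its own and outside the multiplicity procedure of SAP 4.6.

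**What to change.** In SAP 8.4.2, use the withdrawal reason already planned for SAP 5.1 to define rollover for need of rescue, then:

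- (a) report the cumulative incidence of IVIg/PEX use with that rollover as a competing event;
- (b) beside it, show a supportive curve for the composite of IVIg/PEX use or rollover for need of rescue, and do not present (a) alone;
- split the censored counts at Days 57, 71, 85 and 99 into rollover for need of rescue and all other reasons;
- if a median falls after Day 43, say which of the two curves it comes from.

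Leave SAP 8.4.1 as it is. The cost is SAP wording, one extra derivation and one extra descriptive curve, with no new data collection. The result depends on the withdrawal reason being recorded accurately. No rescue or rollover rule changes.
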